7.3.2. Time to Response

Time to response is defined as the interval from randomization to first response (CR or PR) before initiation of new therapy. In the time to response analysis, participants without a response after randomization will be censored at either study withdrawal, initiation of new systemic anti-GVHD therapy, death, relapse, or last response assessment prior to or on the cutoff date, whichever is earliest. Time to response will be summarized for participants who achieve a response using the Kaplan-Meier method. Median time to response and a 95% CI will be estimated.

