7.1. General Considerations

In Part 1, all efficacy analyses will be performed using the safety run-in population. In Part 1 Expansion, all efficacy analyses will be performed using the safety population.

If there are not sufficient data for meaningful statistical inference, the planned analysis will not be performed, and only related summary statistics and/or listings will be provided.

In all efficacy analyses, initiation of new systemic anti-GVHD therapy includes 4 scenarios:

1. Initiation of new anti-GVHD therapy including a higher dose of corticosteroid than that used at Day 1.
2. The need for a second dose increase in corticosteroids.
3. A dose increase in corticosteroids that is not tapered back to the previous dose of corticosteroids within 6 weeks (\pm 2 days) of the increase.
4. Reintroduction of systemic corticosteroids that occurs after complete taper of corticosteroids due to response.

No formal statistical tests will be performed.

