7.3. Analyses of the Secondary Efficacy Parameters

7.3.1. Response Rate

Response rate at 3, 6, and 12 months (Days 90, 180, and 365) is defined as the proportion of participants who achieved a response (CR or PR) at each of these timepoints based on an ITT population.

A participant will not be considered a responder for the analysis of ORR at 3, 6, and 12 months if any of the following events occurred at or prior to the response assessment at the predefined timepoint:

- cGVHD progression per NIH response criteria or initiation of a new systemic therapy for cGVHD

- Evidence of progression of the underlying hematologic disease
- Withdrawal from the study
- Death
- Response assessment missing (not performed) at the predefined timepoint

The proportion of responders will be estimated with 95% CIs. Confidence intervals will be calculated based on the exact method for binomial distributions. Summary statistics will be provided.

Additional analyses may be performed based on evaluable subsets. An evaluable population will also be considered with participants who have completed 3, 6, or 12 months of follow-up as of the cutoff date or discontinued earlier because of new cGVHD progression. Presentations of ORR at Month 3 and Month 6 will include a footnote explaining what "evaluable" means (ie, participants who had at least 3 or 6 months of follow-up as of the cutoff date or discontinued earlier).

Summary statistics and 95% CI will be provided by cohort. The primary comparisons in Part 1 expansion will involve only the 2 itacitinib groups (Treatment Groups A and B) and the corticosteroids-only group (Treatment Group D) as a result of Protocol Amendment 8, in which Treatment Group C (300 mg BID + corticosteroids) was discontinued. Data from Treatment Group C will be presented only as summary statistics and will not be subjected to any statistical comparison.

Pairwise Cochran-Mantel-Haenszel tests will be conducted for Month 6 response rate for each of the 2 itacitinib groups (Treatment Groups A and B) and the corticosteroids-only group (Treatment Group D) as an exploratory analysis.

The secondary endpoints discussed below will be summarized by Treatment Groups A, B, and D using the ITT population for efficacy-related endpoints and all groups for safety-related endpoints.

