APPENDIX A. PLANNED TABLES AND LISTINGS

This appendix provides a list of the planned tables, figures, and listings for the Clinical Study Report. Standard tables will follow the conventions in the Standard Safety Tables v1.4. In-text tables are identical in structure and content to appendix tables but follow a Rich Text Format.

Efficacy will use the safety analysis set as described in Section [5.3](#).

Tables

| Table No. | Title | Population |
|-----------|--|------------|
| 1.1.1.1 | Analysis Populations – Part 1 Expansion | Safety |
| 1.1.1.2 | Analysis Populations – Part 1 and Part 1 Expansion | Safety |
| 1.1.2.1 | Summary of Participant Disposition – Part 1 Expansion | Safety |
| 1.1.2.2 | Summary of Participant Disposition – Part 1 and Part 1 Expansion | Safety |
| 1.1.3.1 | Summary of Protocol Deviations – Part 1 Expansion | Safety |
| 1.1.3.2 | Summary of Protocol Deviations – Part 1 and Part 1 Expansion | Safety |
| 1.2.1.1 | Summary of Demographics – Part 1 Expansion | Safety |
| 1.2.1.2 | Summary of Demographics – Part 1 and Part 1 Expansion | Safety |
| 1.3.1.1.1 | Summary of Baseline Disease Characteristics for Cancer History – Part 1 Expansion | Safety |
| 1.3.1.1.2 | Summary of Baseline Disease Characteristics for Cancer History – Part 1 and Part 1 Expansion | Safety |
| 1.3.1.2.1 | Summary of Baseline Disease Characteristics for GVHD – Part 1 Expansion | Safety |
| 1.3.1.2.2 | Summary of Baseline Disease Characteristics for GVHD – Part 1 and Part 1 Expansion | Safety |
| 1.3.2.1 | Summary of Allogeneic Hematopoietic Stem Cell Transplant History – Part 1 Expansion | Safety |
| 1.3.2.2 | Summary of Allogeneic Hematopoietic Stem Cell Transplant History – Part 1 and Part 1 Expansion | Safety |
| 1.3.2.3 | Summary of Karnofsky Scale | Safety |
| 1.3.3.1 | Summary of Prior Anticancer Therapy – Part 1 Expansion | Safety |
| 1.3.3.2 | Summary of Prior Anticancer Therapy – Part 1 and Part 1 Expansion | Safety |
| 1.4.1.1 | Summary of Prior Medications – Part 1 Expansion | Safety |
| 1.4.1.2 | Summary of Prior Medications – Part 1 and Part 1 Expansion | Safety |
| 1.4.2.1 | Summary of Concomitant Medications – Part 1 Expansion | Safety |
| 1.4.2.2 | Summary of Concomitant Medications – Part 1 and Part 1 Expansion | Safety |
| 1.5.1.1 | Summary of General Medical History – Part 1 and Part 1 Expansion | Safety |
| 1.5.1.2 | Summary of Conditioning and Prophylaxis Therapy – Part 1 and Part 1 Expansion | Safety |

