| 2.2.1 | Summary of Overall Response Rate at Months 3, 6, and 12 | Safety |
| 2.2.2 | Summary of Nonrelapse Mortality Rate | Safety |
| 2.2.3 | Summary of Duration of Response | Safety |
| 2.2.4 | Summary of Time to Response | Safety |
| 2.2.5 | Summary of Relapse Rate of Malignant and Nonmalignant Hematologic Diseases | Safety |
| 2.2.6 | Summary of Time to Primary Hematologic Disease Relapse | Safety |
| 2.2.7 | Summary of Overall Survival | Safety |
| 2.2.8 | Summary of Best Overall Response | Safety |
| 2.2.8.1 | Summary of Best Overall Response by GVHD Organ Involved | Safety |

| Table No. | Title | Population |
|-----------|---|------------|
| 2.2.8.2 | Summary of Best Overall Response for Skin Sclerotic Findings Subgroup | Safety |
| 2.2.9 | Summary of Failure-Free Survival | Safety |
| 2.2.11 | Summary of Number of Participants With $\geq 50\%$ Reduction in Daily Corticosteroid Dose at Day 180 | Safety |
| 2.2.12 | Summary of Participants Successfully Tapered Off All Corticosteroids at Day 180 | Safety |
| 2.2.13 | Summary of Number of Participants With $\geq 50\%$ Reduction in Daily Corticosteroid Dose by (4-Week) Time Interval Up to Month 6 | Safety |
| 2.2.14 | Summary of Participants Successfully Tapered Off All Corticosteroids by (4-Week) Time Interval Up to Month 6 | Safety |
| 3.1.1 | Summary of Itacitinib Exposure, Duration of Exposure, and Dose Adjustment | Safety |
| 3.1.2 | Summary of Itacitinib Compliance | Safety |
| 3.1.3 | Summary of Corticosteroid Exposure, Duration of Exposure, and Dose Adjustment | Safety |
| 3.2.1 | Overall Summary of Treatment-Emergent Adverse Events | Safety |
| 3.2.2 | Summary of Treatment-Emergent Adverse Events by MedDRA System Organ Class and Preferred Term | Safety |
| 3.2.3 | Summary of Treatment-Emergent Adverse Events by MedDRA Preferred Term in Decreasing Order of Frequency | Safety |
| 3.2.4 | Summary of Treatment-Emergent Adverse Events by MedDRA System Organ Class, Preferred Term, and Maximum Severity | Safety |
| 3.2.5 | Summary of Itacitinib Treatment-Related, Treatment-Emergent Adverse Events by MedDRA System Organ Class and Preferred Term | Safety |
| 3.2.6 | Summary of Itacitinib Treatment-Related, Treatment-Emergent Adverse Events by MedDRA Preferred Term in Decreasing Order of Frequency | Safety |
| 3.2.7 | Summary of Itacitinib Treatment-Related, Grade 3 or Higher Treatment-Emergent Adverse Events by MedDRA System Organ Class, and Preferred Term | Safety |

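### SAP 7.3.2 sets a censoring rule for non-responders, then limits the Kaplan-Meier summary of time to response to responders; the estimator and the analysis population each need one stated choice

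*SAP*

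**What the plan says.** **Estimator.** SAP 7.3.2 starts the clock at randomization and stops it at "first response (CR or PR) before initiation of new therapy". It then gives two instructions:

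- "participants without a response after randomization will be censored at either study withdrawal, initiation of new systemic anti-GVHD therapy, death, relapse", or at the last response assessment by the cutoff, whichever comes first.
- "Time to response will be summarized for participants who achieve a response using the Kaplan-Meier method", with a median and 95% CI.

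**Population.** The closing sentence of SAP 7.3.1, which covers the endpoints that follow it, has them summarized for Groups A, B and D "using the ITT population for efficacy-related endpoints and all groups for safety-related endpoints". Protocol 10.4.2.2 agrees. Against this:

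- SAP 7.1: "In Part 1 Expansion, all efficacy analyses will be performed using the safety population". For Part 1 the same section names the safety run-in population, whereas Protocol 10.4.2.1 names ITT.
- SAP Appendix A: "Efficacy will use the safety analysis set as described in Section" 5.3.
- The entry for Table 2.2.4: "Summary of Time to Response | Safety".

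SAP 11.1 states that ITT and the safety set are equivalent. SAP Table 4 and Protocol Table 24 define them differently: ITT is everyone randomized, while safety requires at least one dose and groups participants by the treatment actually received.

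**The concern.** The two instructions in 7.3.2 cannot both operate. The first places non-responders in the analysis; the second removes them.

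Each reading alone also answers a narrower question than a median per treatment group suggests. Among responders only, the median is conditional on responding and exists however few respond. With all participants, death ends the possibility of response, and new therapy ends it by the endpoint's own definition. Relapse requires withdrawal from study treatment (Protocol 7.1.1). Censoring these participants treats them as still able to respond later. The SAP handles similar events differently elsewhere: section 6.4 treats progression or new therapy, relapse and death as competing risks for steroid reduction, and 7.3.6 uses cumulative incidence for nonrelapse mortality.

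What is at stake is the comparability of the medians across Groups A, B and D. Protocol 6.1.1.4 says descriptive summaries of other secondary endpoints are taken into account when the Part 2 dose is chosen.

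**Working it through.** The documents give no expected median or event count for this endpoint, so there is no planned figure to reproduce. The calculation below only shows size.

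**Inputs**

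- Horizon T = 180 days, which SAP 7.3.1 equates with Month 6. Group size is up to 35 (SAP 3.3.2).
- Response by Day 180 (c1), from SAP Table 3: 18/35 and 22/35 (ends of the corticosteroids-only columns) and 25/35 (lowest itacitinib row). These are Month 6 rates standing in for cumulative first response, which is at least as high.
- Competing events (death, relapse or new therapy) by Day 180 (c2): 5%, 15% and 25%. These are assumptions; the documents give no such rates.

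**Formulas, constant hazards**

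- Total hazard h = −ln(1 − c1 − c2)/T; response share a = c1/(c1 + c2).
- Kaplan-Meier median, competing events censored: ln 2/(a·h).
- Cumulative-incidence median: −ln(1 − 0.5/a)/h.
- Median among those responding by Day 180: −ln(1 − (c1 + c2)/2)/h.

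**One case in full** (c1 = 25/35 = 0.714, c2 = 0.05): h = −ln(0.2357)/180 = 0.00803 per day and a = 0.714/0.764 = 0.935. The three medians are 92.4 days (Kaplan-Meier), 95.4 (cumulative incidence) and 60.0 (responders only).

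| Responding | c2 | KM median | Cumulative-incidence median | KM earlier by | Responders-only median | KM minus responders-only |
|---|---|---|---|---|---|---|
| 25/35 | 5% | 92.4 | 95.4 | 3.0 | 60.0 | 32.4 |
| 25/35 | 15% | 75.6 | 83.7 | 8.1 | 51.0 | 24.6 |
| 25/35 | 25% | 50.5 | 60.7 | 10.2 | 35.5 | 15.0 |
| 22/35 | 5% | 118.7 | 123.1 | 4.4 | 65.7 | 52.9 |
| 22/35 | 15% | 102.5 | 115.3 | 12.8 | 58.9 | 43.6 |
| 22/35 | 25% | 82.7 | 102.5 | 19.8 | 49.4 | 33.3 |
| 18/35 | 5% | 164.8 | 172.3 | 7.6 | 71.8 | 93.0 |
| 18/35 | 15% | 147.6 | 171.2 | 23.5 | 66.6 | 81.1 |
| 18/35 | 25% | 128.3 | 169.3 | 41.0 | 60.0 | 68.3 |

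(Days; differences taken before rounding.) In every row the choice between the two readings of 7.3.2 moves the median more than the choice between Kaplan-Meier and cumulative incidence.

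**Sensitivity to hazard shape.** If the response hazard is five times higher before Day 84 than after, Kaplan-Meier is earlier by 1.2/3.7/5.6 days at 25/35, 1.7/5.4/9.1 at 22/35 and 15.2/48.0/68.0 at 18/35 (c2 = 5/15/25%). At 18/35 (51%) the curve is nearly flat where it crosses one half, so any median there is unstable.

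**What the Kaplan-Meier median does not show.** Fix the response hazard at 0.00621 per day. The Kaplan-Meier median is ln 2/0.00621 = 111.6 days whatever the competing hazard. With competing hazards of 0.0005 and 0.003 per day, 65% and 55% respond by Day 180, and the cumulative-incidence medians are 116 and 147 days.

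**A median although fewer than half responded.** In 20,000 simulated groups of 35 under constant hazards, Kaplan-Meier reached a median by Day 180 although fewer than half had responded in about 6/21/33% of runs at 18/35, 2/5/6% at 22/35 and under 0.5% at 25/35 (c2 = 5/15/25%).

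**The case against.** **The numerical effect can be small.** This stands. Two of the three groups summarized receive itacitinib, and the itacitinib rows of SAP Table 3 run from 25/35 to 30/35. At 30/35 the Kaplan-Meier median is earlier by only 1.5 days with 5% competing events and 2.5 with 10%. Treatment visits are mostly 28 days apart, so gaps of this size may not show. A reader might take the 41- or 68-day gap, or the 33% of runs, as typical. They arise only with response near 50% and the highest assumed competing rate.

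**Neither median is wrong in itself.** This also stands. The responders-only median is a proper description of responders. The Kaplan-Meier median is a net quantity under independent censoring, and it is too early only if the target is the time by which half the group has responded. A reader might infer that more competing events shorten the Kaplan-Meier median; at a fixed response hazard they do not.

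**The text does not dictate the competing events.** This stands in part. "A participant will not be considered a responder for the analysis of ORR at 3, 6, and 12 months" introduces a list of events for fixed-timepoint response rates, not for 7.3.2. The 7.3.2 definition bars response after new therapy but not after relapse, so treating relapse as competing is a choice. Sections 6.4 and 7.3.6 concern other endpoints, and 7.3.3 censors relapse, so the SAP has no general rule that was broken.

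**Other tables supply what the median omits.** Largely true. Table 2.2.1 gives response at Months 3, 6 and 12, and Table 2.2.8 gives best overall response, which is close to the proportion who ever respond.

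**The population conflict reaches beyond this endpoint, and its effect is unknown.** True. Protocol 8.1.2 starts treatment within 2 days of randomization, and a dose of reference therapy suffices for the safety set, so the two sets may coincide in the data.

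None of this removes the contradiction inside 7.3.2 or the one over population.

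**Conclusion.** The point holds as a defect of specification. SAP 7.3.2 does not determine its own analysis, and either reading can be defended from the text. With 5% competing events the readings differ by 32 days at 25/35 responding and 93 days at 18/35. The difference between Kaplan-Meier and cumulative incidence is secondary: about 3 to 10 days at 25/35, 4 to 20 at 22/35 and 8 to 41 at 18/35. These figures rest on assumed competing rates, constant hazards and Month 6 response as a proxy for first response.

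The population is contradictory as written, and the equivalence in SAP 11.1 does not follow from the definitions. How many participants this affects cannot be told from the documents.

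A reader might infer that the Part 2 dose decision is compromised. The documents do not support that: the endpoint is descriptive and untested, SAP 7.2 rests dose selection primarily on adverse events, the response rates of 7.3.1 do not depend on 7.3.2, and time to response is not a Part 2 endpoint. Priority is low to modest.

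**What to change.** In SAP 7.3.2:

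- Estimate the cumulative incidence of first response in all participants of one stated population. Treat death, relapse and new systemic therapy as competing events; censor only at study withdrawal and last assessment.
- Report it at Months 3, 6 and 12, with the median where the curve reaches 50% and a statement that it was not reached otherwise.
- If a responders-only median is wanted, give it as a plain description, labelled as conditional on response, without censoring.

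For the population, ITT suits a clock that starts at randomization and matches SAP 7.3.1 and Protocol 10.4.2.2. Then correct SAP 7.1, 11.1, Appendix A and the population column of Table 2.2.4.

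The cost is SAP wording and a standard software option, with no new data and no new table. Compared with either current reading, reported medians will be later or not reached.

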7.3.3. Duration of Response

Duration of response is defined as the interval between the date of initial documentation of response (CR or PR) and the date of cGVHD progression per NIH response criteria, initiation of new systemic cGVHD therapy, or death. Participants experiencing relapse of underlying hematologic relapse will be censored at the date of relapse.

Duration of response will be summarized for participants who achieve a response. Duration of response will be assessed using the Kaplan-Meier method for participants who achieve a response. Median duration and a 95% CI will be estimated. Participants who are still responding at the time of database lock or discontinuation will be right-censored at the time of last valid response assessment.

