7. DISCONTINUATION OF STUDY TREATMENT AND PARTICIPANT DISCONTINUATION/WITHDRAWAL

7.1. Discontinuation of Study Treatment

The decision to discontinue study treatment will not constitute study completion. In the event the decision is made to discontinue study treatment, the treatment period will be considered complete, and the follow-up period will begin.

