8.8.2. Post-Treatment GVHD Follow-Up

Participants who complete itacitinib/placebo taper after an initial response (CR or PR) or discontinue early for reasons other than cGVHD progression and with no requirement for new

cGVHD therapy will be followed until cGVHD progression, initiation of a new cGVHD therapy, initiation of treatment for relapse/recurrence of the underlying hematologic disease, death, or end of study and for a maximum of 24 months from Day 1, at which point the participant may enter survival follow-up. The participant will be followed at clinic visits every 28 days (\pm 7 days) after the safety follow-up visit up to 1 year from Day 1 and then every 8 weeks (\pm 7 days) up to 2 years from Day 1.

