8.8.3. Survival Follow-Up

Once a participant has completed the post-treatment GVHD follow-up (ie, 24 months from Day 1) or has confirmed GVHD progression or starts a new GVHD therapy, or experiences relapse/recurrence of the underlying hematologic disease, then the participant moves into the survival follow-up period and should be contacted by telephone, email, or visit at least every 8 weeks to assess for survival status until death or withdrawal of consent, whichever occurs first.

For participants having entered the survival follow-up period of the study, the site will use continuing participant records to supply data on subsequent treatment regimens, GVHD assessments (if discontinued treatment for a reason other than progression), and OS in the eCRF. For participants who do not intend to return to the study investigator for their ongoing care, follow-up should be maintained by phone contact, patient records, and public records/databases at intervals of no longer than 8 weeks.

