10.4.2.2. Part 1 Expansion

For Part 1 Expansion, the key secondary endpoints are response rate at Month 3 and Month 6, which are defined as the proportion of participants who demonstrate a CR or PR at each timepoint. The analysis will be conducted once the last participant completes Month 3 and Month 6 visits or withdraws from the study by treatment group for response rates at Month 3 and

Month 6, respectively. Summary statistics and 95% CI will be provided by cohort. The primary comparisons in Part 1 expansion will involve only the 2 itacitinib groups (A and B) and the corticosteroid alone group (D) as a result of Protocol Amendment 8, which discontinued Group C (300 mg BID + corticosteroid). Group C data will be presented only as summary statistics but will not be subjected to any statistical comparison.

Pairwise CMH tests will be conducted to Month 6 response rate for each of the 2 itacitinib groups (Treatment Group A and B) and the corticosteroids-only group (Treatment Group D) as an exploratory analysis.

The following secondary endpoints will be summarized by Treatment Groups A, B, and D using the ITT population for efficacy-related endpoints and all groups for safety-related endpoints:

- Response rate at 12 months, defined as the proportion of participants who achieved response (CR or PR) at Month 12.
- Time to response, defined as the interval between randomization and first response.
- DoR, defined as the interval between first response and cGVHD progression, death, or initiation of new systemic cGVHD therapy.
- OS, defined as the interval between the date of randomization and the date of death due to any cause.
- NRM, defined as the proportion of participants who died due to causes other than a relapse of their primary hematologic disease.
- Proportion of participants with ≥ 50% reduction in daily corticosteroid dose at Day 180.
- Proportion of participants successfully tapered off all corticosteroids at Day 180.
- Relapse rate of malignant and nonmalignant hematologic diseases, defined as the proportion of participants whose underlying disease relapses.
- Time to primary hematologic disease relapse, defined as the interval between the date of randomization and the date of relapse. Data from clinical safety assessments (eg, AEs, infections) will be listed and tabulated by treatment group.

10.4.2.3. Part 2

The following secondary endpoints will be summarized by treatment group using the ITT population:

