6.2. Disposition of Participants

The number and percentage of participants who were randomized, treated, completed treatment, discontinued study treatment with a primary reason for discontinuation, and withdrew from the study with a primary reason for withdrawal will be summarized for the safety run-in population and the Part 1 expansion population.

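### SAP 7.3.3 censors duration of response at an undefined discontinuation; if that means stopping treatment, failures that the endpoint counts and the protocol collects afterwards are left out

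*SAP*

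**What the plan says.** Protocol 10.4.2.2 gives the endpoint: "DoR, defined as the interval between first response and cGVHD progression, death, or initiation of new systemic cGVHD therapy". SAP 7.3.3 uses the same three end events, estimates DoR by Kaplan-Meier in responders, and has two censoring rules. One covers hematologic relapse: "Participants experiencing relapse of underlying hematologic relapse will be censored at the date of relapse". The other is the rule at issue: "Participants who are still responding at the time of database lock or discontinuation will be right-censored at the time of last valid response assessment".

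The protocol separates the end of treatment from the end of the study. Section 7.1 states: "The decision to discontinue study treatment will not constitute study completion". Under 8.8.2, participants who finish the itacitinib taper after a response, or who stop early without progression and without needing new cGVHD therapy, "will be followed until cGVHD progression, initiation of a new cGVHD therapy", among other end points. This clinic follow-up runs "for a maximum of 24 months from Day 1, at which point the participant may enter survival follow-up". In survival follow-up (8.8.3), sites still "supply data on subsequent treatment regimens, GVHD assessments (if discontinued treatment for a reason other than progression), and OS in the eCRF".

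**The concern.** If discontinuation means stopping treatment, the rule closes a responder's record at a point where the endpoint is still open and data are still being gathered. Progression, new therapy and death after that point fall outside the estimate. The result is response up to stopping treatment, reported under the name DoR.

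Stopping may also be related to failure. Protocol 7.1.1 requires treatment to stop when additional systemic therapy is being considered for lack of benefit, so the start of that therapy, which is the DoR event, can come after the stop. Response is scored against Day 1 (Protocol 8.2.2), so a participant can worsen from their best state and still be a partial responder when treatment stops.

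Protocol 6.1.1.4 lets descriptive summaries of the other secondary endpoints contribute to the choice of the Part 2 dose. It therefore matters that DoR means the same thing in Groups A, B and D.

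**Working it through.** **1. Which meaning of discontinuation?**

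For stopping treatment:
- SAP 6.2 uses separate words for the two events: "discontinued study treatment with a primary reason for discontinuation, and withdrew from the study with a primary reason for withdrawal".
- SAP 7.3.2, the section just before, censors time to response at study withdrawal. SAP 7.3.1 also names withdrawal from the study.
- SAP 7.3.1 describes evaluable participants as including those who discontinued because of new cGVHD progression, which is a treatment-stopping reason in Protocol 7.1.1.
- Protocol 8.7 speaks of permanently discontinuing study drug, for both early stopping and completed treatment.

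For leaving the study:
- Protocol 4.2 speaks of participants who discontinued the study early.
- A second sentence in SAP 7.3.1 sets discontinued against having enough follow-up.
- SAP 7.3.3 pairs the word with database lock, which is an end of observation.

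The first reading is likelier. Neither is stated.

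**2. Does it fit the other SAP rules?** SAP 7.1, scenario 4, applies to all efficacy analyses and treats restarting systemic steroids after a full taper as new therapy, hence a DoR event. In Group D steroids are the only study treatment, so this event can occur only after all study treatment has ended. If finishing the taper counts as discontinuation, the event can never be counted in Group D, yet it can be in Groups A and B while itacitinib continues. SAP 11.1 lists no change to DoR censoring from the protocol.

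**3. Direction and size.** The documents give no median, event count or stopping rate for DoR, so there is no figure to reproduce. All rates below are assumptions.

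Let λ1 be the failure hazard on treatment, d the hazard of stopping while in response, and λ2 = HR × λ1 the failure hazard after stopping.
- Kaplan-Meier censored at stopping estimates exp(−λ1 t), whatever happens later.
- Counting all events gives S(t) = exp(−(λ1+d)t) + d[exp(−λ2 t) − exp(−(λ1+d)t)]/(λ1+d−λ2).

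Example: on-treatment median 12 months, 40% stopping by month 12 (among those who would not otherwise have failed), HR 2. Then λ1 = ln 2/12 = 0.0578, d = −ln(0.6)/12 = 0.0426, λ2 = 0.1155 and λ1+d = 0.1003. At 12 months S = 0.300 + 0.0426 × (0.250 − 0.300)/(0.1003 − 0.1155) = 0.300 + 0.140 = 0.440, against 0.500 with censoring at stopping.

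Median DoR in months when all events are counted:

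| Median with censoring at stopping | Stopping by month 12 | HR 0.5 | HR 1 | HR 2 | HR 3 |
|---|---|---|---|---|---|
| 12.0 | 20% | 12.8 | 12.0 | 11.1 | 10.6 |
| 12.0 | 40% | 13.9 | 12.0 | 10.3 | 9.5 |
| 18.0 | 20% | 19.8 | 18.0 | 16.1 | 15.1 |
| 18.0 | 40% | 22.2 | 18.0 | 14.7 | 13.1 |

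The adverse extreme is a fraction f of failures censored just before they occur. A true median of 12 months then reads as 12/(1−f): 13.3, 15.0 or 17.1 months for f = 0.1, 0.2 or 0.3.

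**The case against.** The strongest reply is that the SAP meant leaving the study. Then the rule is ordinary censoring and nothing collected is lost. Scenario 4 of SAP 7.1 points that way, since it expects failures after the steroid taper to count. The sentence also censors at the last valid response assessment, without limiting this to assessments before treatment stopped, and Table 4 of the protocol schedules response assessments in follow-up. This stands as far as it goes: the meaning is unsettled. It does not rescue the sentence, because two programmers could follow it and produce different DoR curves.

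A reader might infer that reported DoR must come out too long. The documents do not support that. Censoring removes later event-free time as well as later failures, so the error is upward only if risk rises after stopping. Lower risk is plausible after a planned taper, which Protocol 6.1.1.6 reserves for responders who have been off therapeutic steroids and other systemic immunosuppression for at least 3 months.

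A reader might also infer that Group D is censored earlier than Groups A and B. That holds only if finishing the steroid taper counts as discontinuation. SAP 6.2 lists completed treatment apart from discontinued treatment, and scenario 4 implies that failures after the taper should count.

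The consequence is also limited. DoR is a descriptive secondary endpoint in the responders among at most 35 participants per group, SAP 3.2 plans no formal test, and SAP 7.2 bases dose selection primarily on adverse events.

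**Conclusion.** The point holds as an undefined censoring rule which, on its likelier reading, conflicts with the DoR definition and with SAP 7.1. Progression, new systemic therapy or death at or before stopping is counted on either reading; what is at risk is events afterwards. Clinic GVHD follow-up is limited to participants who stopped without progression or need for new therapy, and to 24 months from Day 1.

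The size cannot be determined from the documents. Under the assumed rates, counting all events moves a 12-month median to between 9.5 and 13.9 months, with no change at equal risk. These figures use constant hazards from first response, although the protocol allows itacitinib taper only from Day 180 in sustained CR and otherwise from Day 365. They show direction and are not a forecast. Unequal effect between groups is possible but not established.

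**What to change.** Replace the sentence in SAP 7.3.3 with:

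*Participants without progression, new systemic cGVHD therapy or death are censored at the last valid cGVHD response assessment on or before the cutoff, study withdrawal or loss to follow-up, including assessments in post-treatment GVHD follow-up; stopping or completing study treatment is not a reason for censoring.*

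Keep the separate rule for hematologic relapse. If an on-treatment view is wanted, show censoring at treatment discontinuation as a sensitivity analysis only.

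The cost is one sentence and a small programming change, using data that the protocol already collects. DoR may come out less favourable. If the sponsor meant study withdrawal all along, the change only makes that clear.
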